#### **10.5.5. Lipoprotein Evaluations**

Serum chemistry-based assessments are the standard safety tool for monitoring subjects’ serum lipids. Additional lipoprotein samples, separate from the serum chemistry samples, will be obtained and assayed in addition to the serum chemistry panel lipid assay.

The lipoprotein analyte values, change from baseline, and percentage change from baseline will be summarized by treatment group for the lipoprotein analytes. Baseline is defined as the last fasting assessment before treatment. This analysis will use only samples that have a confirmed fasting of approximately 8 hours or more before their visit.

Analyses of quantitative lipoprotein analytes will be carried out using MMRM as described in the General Statistical Methods ([Section 4](#)).

Subgroup analysis by statin use (no concomitant statin use, statin use started prior to first dose of investigational product and statin use started after first dose of investigational product) will be performed. In addition to statin use, similar subgroup analyses will be performed by use of other antihyperlipidemic drugs. Only descriptive statistics will be provided.

#### 10.5.6. Renal Function Evaluations

Summary statistics for absolute values, change from baseline, and percent change from baseline to each on-study evaluation visit, as well as worst and last postbaseline values, will be presented for eGFR, serum creatinine, and urinary albumin to creatinine ratio as specified in [Table 8](#). The summary will also be repeated for baseline CKD stage, baseline diabetes status (history of diabetes mellitus at baseline or on antidiabetic medications at baseline with indication for diabetes mellitus or baseline HbA1Cc  $\geq 6.5\%$ ), and baseline fibrosis stage. The 95% CIs for the difference in mean change will be also presented.

Annualized change in eGFR (mL/min/1.73 m^2/yr) will be summarized descriptively. The proportion of subjects that experience rapid eGFR decline (defined as  $>4$  mL/min/1.73 m^2/yr) will be presented.

Plots will be created to show mean laboratory (kidney function) data change from baseline over time for eGFR, serum creatinine, and as appropriate other markers of kidney function or injury such as Albumin to creatinine ratio. An additional plot for the percent change from baseline over time will be created only for serum creatinine.

Descriptive statistics for eGFR will be presented for subgroups by baseline CKD stage, baseline diabetes status, and baseline fibrosis stage.

Renal safety parameters serum creatinine and eGFR will also be utilized to present analyses of the worst change from baseline at any post-baseline visit, including risk differences and 95% CIs (using CMH method). The following change from baseline categories will be analyzed:

- Creatinine ( $\geq 1.5$  x BL,  $\geq 2.0$  x BL,  $\geq 3.0$  x BL)
- eGFR ( $\geq 25\%$  decrease from BL,  $\geq 50\%$  decrease from BL,  $\geq 75\%$  decrease from BL)

A listing will be created to display subjects with any post-baseline serum creatinine value  $\geq 2.0$  x BL or eGFR  $\geq 50\%$  decrease from BL.

A summary will also be provided based only on the last on-treatment measurements recorded for serum creatinine and eGFR, including risk differences and 95% CIs (using CMH method). The following change from baseline categories will be analyzed:

- Creatinine ( $\geq 1.5$  x BL,  $\geq 2.0$  x BL)
- eGFR ( $\geq 25\%$  decrease from BL,  $\geq 50\%$  decrease from BL)

In addition, shifts from baseline to each on-study evaluation will be presented for eGFR, based on the standard eGFR categories as defined in [Table 7](#).

**Table 7: Stages of CKD**

CKD Stage	Glomerular Filtration Rate (mL/min/1.73 m2)
G1/Normal	≥90
G2	60 – 89
G3	30 – 59
G3a	45-59
G3b	30-44
G4/5	<30

CKD = chronic kidney disease; G = Group

Shifts from baseline to Month 18 in urinary albumin to creatinine ratio (mg/g) will also be presented using the categories defined in [Table 8](#).

**Table 8: Cutoffs of Albumin to Creatinine Ratio**

Category	Albumin to Creatinine Ratio (mg/g)
Normal	<30
Microalbuminuria	30 – 300
Macroalbuminuria	>300

## 10.6. Pregnancies

If any subject gets pregnant during the course of the study, a by-subject data listing will be provided including all data on the Pregnancy eCRF.

## 10.7. Vital Signs

The results, change and percentage change from Baseline to each on-study evaluation visit will be summarized for oral temperature, sitting heart rate, and respiratory rate.

All vital sign data will be presented in by-subject data listings.

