The FLINT study demonstrated that OCA was superior to placebo in improving not only the key histologic features important in the underlying pathophysiology of the disease (inflammation, ballooning, and steatosis), but notably that OCA was superior to placebo in improving fibrosis, a strong predictor of liver-related death. OCA treatment was also associated with improvement in markers of hepatocellular injury and some cardiometabolic features, including weight and systolic blood pressure. Salutory effects on weight and blood pressure are important considerations since patients with NASH present with higher cardiovascular risk given the comorbidities of obesity and diabetes. On average, low-density lipoprotein (LDL) cholesterol demonstrated a modest but significant increase in subjects treated with OCA compared to placebo; however, this increase was reversed and LDL cholesterol returned to below baseline levels in subjects who initiated statin therapy. The change in lipid profile, which was attenuated with continued treatment and reversed post-treatment, needs to be further investigated mechanistically and with respect to clinical management with standard of care statin therapy.

The general adverse event (AE) profile was similar across both groups, with the exception of pruritus. Pruritus occurred more frequently in the OCA-treated subjects (23% OCA versus 6% placebo), led to 1 discontinuation, and was generally mild and moderate in severity. Otherwise, pruritus was well managed with the use of antipruritic medications and treatment interruption.

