9.9.4. Day 1 Procedures (Randomization)

Day 1 Visit procedures for all subjects are as follows:

- Verify that the subject has fasted for at least 8 hours
 - Record fasting status in the source and CRF
 - If the subject reports having eaten within 8 hours, document accordingly in the source and CRF and remind the subject that fasting is required before all study visits after screening.
- Perform a standard 12-lead electrocardiogram (ECG)
- Review inclusion and exclusion criteria for eligibility
- [REDACTED] and vital signs (body temperature, sitting heart rate, respiratory rate, and sitting blood pressure)
- [REDACTED]

- Determine alcohol consumption (AUDIT questionnaire), smoking habits, and caffeine consumption
- Educate subjects about signs and symptoms of potential hepatic injury or decompensation
- Evaluate signs and symptoms of potential hepatic injury or decompensation (Appendix C) and assess subjects per Potential DILI Management (Figure 2) and Progression to Cirrhosis (Figure 3) Algorithms
 - In subjects who progress to cirrhosis and have a CP score <7 , 1 PK blood sample will be obtained at the next scheduled visit prior to dose adjustment. Subjects who discontinue investigational product due to progression to cirrhosis and Child Pugh score ≥ 7 or due to hepatic injury, will provide a PK blood sample if the site visit is within 7 days from dose interruption or discontinuation. The time of the last dose of investigational product prior to the PK blood sample will be reported.
- [REDACTED]
- Assess and record any pretreatment-emergent AEs
- Record prior (if within 6 months of Day 1) and current concomitant medications
- Randomize the subject only if s/he meets all inclusion criteria and no exclusion criteria
- If hepatobiliary ultrasound for [REDACTED] and for gallbladder assessment was not performed at Screening and the historic ultrasound is >3 months from Day 1, perform a hepatobiliary ultrasound.
- [REDACTED]
 - [REDACTED]
 - Serum chemistry, hematology, and coagulation
 - Thyroid hormones
 - Free fatty acids
 - Insulin, c-peptide, and HOMA-IR
 - Glucose and HbA1c
 - Apoptosis markers (CK-18 M30 and CK-18 M65)
 - Noninvasive assessments of liver fibrosis: ELF, Fibrotest/Fibrosure
 - Inflammation marker (hs-CRP)
 - [REDACTED]
- Calculations will be performed by the Sponsor or designee for:
 - MELD score

- [REDACTED]
- Obtain urine sample for urinalysis
- Perform a urine-based β -hCG pregnancy test for females of childbearing potential

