15.2.3. Vital Signs

Vital signs will be assessed at the visits specified in [Table 1](#). Vital signs include body temperature, sitting heart rate, respiratory rate, and sitting blood pressure. When taking heart rate, respiratory rate, and blood pressure readings, subjects should be seated quietly for a minimum of 3 minutes before the readings are taken.

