16.9.7. Additional Safety Analysis

16.9.7.1. Vital Signs

The results and change from Baseline to each on-study evaluation visit will be summarized for body temperature, sitting heart rate, and respiratory rate. Baseline is defined as the mean of all available evaluations before treatment.

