#### **2.1.2.4. Safety Objectives Assessed at End of Study**

- To evaluate the effect of OCA compared to placebo on:
  - Incidence, exposure adjusted incidence rate and time to treatment-emergent pruritus
  - Incidence, exposure adjusted incidence and time to adjudicated cardiovascular events
  - Incidence and exposure adjusted incidence adjudicated acute kidney injury (AKI)

- Incidence, exposure adjusted incidence and time to adjudicated events of hepatic injury
- Long-term safety and tolerability (TEAEs, AESIs, ECGs, vital signs, clinical laboratory assessments)

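### The vital-sign summaries in SAP 10.7 and protocol 16.9.7.1 leave out sitting blood pressure, although the protocol defines it as a vital sign and measures it throughout the study

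*SAP*

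**What the plan says.** Protocol 15.2.3 defines the set: "Vital signs include body temperature, sitting heart rate, respiratory rate, and sitting blood pressure". The Schedule of Study Procedures (Table 1, footnote g) repeats it, and the visit sections apply it. Day 1, for example, calls for "vital signs (body temperature, sitting heart rate, respiratory rate, and sitting blood pressure". The same four measures are named for Screening, Months 1 to 18, the semi-annual visits, Month 48 and the EOS/EOT visit (protocol 9.9.3 to 9.9.9).

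The analysis sections name fewer. Under protocol 16.9.7.1, results and change from baseline "will be summarized for body temperature, sitting heart rate, and respiratory rate". Under SAP 10.7, results, change and percentage change "will be summarized for oral temperature, sitting heart rate, and respiratory rate". SAP 10.7 then adds: "All vital sign data will be presented in by-subject data listings".

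The SAP's End of Study safety objectives (2.1.2.4) include the comparison of OCA with placebo on "Long-term safety and tolerability (TEAEs, AESIs, ECGs, vital signs, clinical laboratory assessments". The safety paragraph of the protocol synopsis likewise says that vital signs will be compared between the OCA groups and placebo at Month 18 and at EOS. Neither place says which vital signs are meant.

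**The concern.** Four measures are collected under the name of vital signs and three are summarised. The one left out is blood pressure. A programmer who works from SAP 10.7 would tabulate temperature, heart rate and respiratory rate by arm and would only list blood pressure.

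The documents themselves give blood pressure some weight. Protocol 5.3 reports that in the Phase 2 NASH study OCA was associated with improvement in "some cardiometabolic features, including weight and systolic blood pressure", and it treats such effects as important because of the higher cardiovascular risk of patients with NASH. Protocol 5.5 describes a rise in LDL cholesterol and a fall in HDL cholesterol on OCA and says that the cardiovascular effect cannot yet be judged. Adjudicated cardiovascular events are an End of Study safety objective. Blood pressure by arm and visit would be useful context for those events, and a listing of individual values does not provide it.

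**Working it through.** **Comparison of the lists.** There is no figure of the plan's own to reproduce, so the check sets the text side by side.

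| Measure | Defined and collected (protocol 15.2.3, Table 1) | Summarised, protocol 16.9.7.1 | Summarised, SAP 10.7 |
|---|---|---|---|
| Temperature | yes | yes (body) | yes (oral) |
| Sitting heart rate | yes | yes | yes |
| Respiratory rate | yes | yes | yes |
| Sitting blood pressure | yes | no | no (listing only) |

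Both summary sentences are complete and closed. They show no redaction mark, no gap, and no wording that makes the list an example. The omission therefore belongs to the plan and was not produced by the reading of the PDF.

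**Does other visible text fill the gap?**
- SAP section 4 says how continuous variables are summarised, not which ones. SAP 2.4 and the synopsis refer to vital signs only as a class. A general statement does not override a specific closed list.
- Protocol 16.9.4 summarises cardiovascular risk scores by treatment group. Systolic pressure is one input among several, so a shift in pressure cannot be read from a score.
- The TEAE tables (SAP 10.3) would show blood pressure events that were reported as adverse events, but not mean values or changes by visit.
- Otherwise blood pressure appears only in the eligibility criteria and the background.

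Within the visible text, no section gives blood pressure by arm over time.

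**What precision the data could support.** Planned enrolment is 2370 in a 1:1:1 ratio, and 2370/3 = 790 per arm (all fibrosis stages, as in the Safety Population). The documents give no SD for the change in blood pressure, so 12 to 20 mmHg is an assumption. For a difference between two arms with n subjects each, the 95% CI half-width is 1.96 × SD × √(2/n).

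- n = 790: √(2/790) = 0.0503
  - SD 12: 1.96 × 12 × 0.0503 = 1.2 mmHg
  - SD 15: 1.96 × 15 × 0.0503 = 1.5 mmHg
  - SD 20: 1.96 × 20 × 0.0503 = 2.0 mmHg
- n = 400 (assumed, to allow for loss at late visits): √(2/400) = 0.0707
  - SD 15: 1.96 × 15 × 0.0707 = 2.1 mmHg

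These figures describe what the data could show. SAP 10.7 plans no confidence interval for an arm difference for any vital sign, and SAP section 10 plans no inferential comparison of safety endpoints unless otherwise specified.

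**The case against.** The strongest answer is that much of the plan cannot be seen. In SAP 6.4.6 only the subsection on MELD is visible, and 10.4.9.3, within the cardiovascular risk section, is missing. Hidden text evidently covers related measures: SAP Appendix A sets baselines for anthropometric measures and for a cardiovascular assessment, yet no visible SAP section describes their analysis. Body weight shares a row with vital signs in Table 1 and is also absent from SAP 10.7, and protocol 5.3 groups weight with systolic pressure. Two documents that omit the same item may reflect a deliberate placement in a cardiometabolic section as easily as an oversight. This part stands. It means that one cannot say blood pressure is unsummarised in the plan as a whole. It does not repair SAP 10.7, which neither includes blood pressure nor points to another section.

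A second answer is that nothing depends on the table. Cardiovascular safety is assessed directly through adjudicated events with their own time-to-event analyses and subgroups (SAP 10.4.9.1), and the blood pressure values are collected and listed, so they are not lost. This also stands, and it keeps the point minor.

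A third is that the synopsis and SAP 2.4 already cover all vital signs. This does not carry: those passages name the class, while the operative sections name the parameters.

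**Conclusion.** Within the vital-sign safety section, blood pressure has no summary by treatment group. It appears only in by-subject listings, although the protocol defines it as a vital sign and vital signs are part of the stated comparison with placebo. That rests on fully visible text and on no numerical assumption.

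A reader might infer two stronger things. One is that blood pressure will not be compared by arm anywhere in the report. The documents do not support this, because the unseen parts of SAP 6.4.6 and section 10.4.9.3 may contain such a summary. The other is that cardiovascular events cannot be interpreted without this table, or that blood pressure is the vital sign that matters most for cardiovascular safety. The documents show that blood pressure is relevant, but they do not rank the vital signs and no cardiovascular analysis depends on the table.

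The severity is minor. The precision figures (about 1.2 to 2.0 mmHg with 790 per arm, about 2.1 mmHg with 400 per arm at SD 15) rest on assumed SDs, on planned enrolment or an assumed later number, and on an interval that the section does not plan.

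**What to change.** In SAP 10.7, add sitting systolic and diastolic blood pressure to the summarised parameters: value, change and percentage change from baseline, by visit and treatment group, in the Safety Population, descriptive only. If another section already gives this, a one-line cross-reference is enough. Align protocol 16.9.7.1 at the next revision; a descriptive table does not need an amendment of its own. The same edit can settle whether the temperature parameter is called body or oral.

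The cost is small. The data are already collected, and SAP 4.2 and Appendix A already define the vital-sign baseline as the mean of the pre-treatment evaluations. The change adds two parameters to a planned summary and uses no alpha.

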## 10.8. Electrocardiograms

The central read ECG data will be analyzed based on methodology recommended in the International Conference on Harmonisation (ICH) E14 guideline, The Clinical Evaluation of QT/QTc Interval Prolongation and Proarrhythmic Potential for Nonantiarrhythmic Drugs.

Baseline is defined as the mean of all available evaluations before treatment. Descriptive statistics of ECG parameters (time between 2 consecutive R waves [RR], PR, QRS, QT, and QT interval corrected by the Fridericia’s formula [QTcF]) at baseline and at each post-baseline timepoint will be summarized by treatment group; absolute changes from baseline will also be summarized.

A categorical summary of abnormal QTcF values will be presented by treatment group. The number of subjects with values of >450 msec, >480 msec, and >500 msec will be presented, and

the number of subjects with change from baseline values of >30 msec and >60 msec will also be presented.

Overall interpretation results for ECGs and the investigator interpretation results are collected as normal, abnormal not clinically significant (NCS), and abnormal clinically significant (CS). Subjects whose interpretations shift from normal to abnormal (CS or NCS) will be listed separately, including description of the abnormality and any associated comments.

All ECG results will be presented in by-subject data listings.

## 11. CHANGES TO PLANNED ANALYSES

As of this date, the Month 18 IA analyses for resubmission have been conducted per FDA agreement following SAP addendum V2.0 (dated 25April 2022).

The key changes for this SAP are summarized in the table below:

Key Changes	Rationale	Contents
Changed to one clinic outcome interim analysis at 66% of information fraction	One IA 66% information fraction will balance preserving type I error with obtaining a reasonable estimate of clinical outcomes efficacy while minimizing the potential for any increases of patient discontinuations as a result of availability of commercial OCA should the agency grant approval of OCA for the NASH indication.	Changed to IA at 66% of information fraction from two IAs at 50% and 80% before end of study analysis under section 2.2.  Updated Alpha spending and HR boundaries under section 3.2.
Added Estimands for clinical composite outcomes for end of study analyses	Per current regulatory agencies, the estimand approach following the ICH request for the definition of Estimands should be defined in clinical trials and the statistical analysis plan.	Estimands including strategies to handle the intercurrent events are provided under section 2.3.2.1.
Updated monitoring plan	The monitoring of clinical outcome events will be used to set up the timeline to initiate and prepare for IA and end of study analysis per FDA's comment.	Updated Monitoring plan for IA and End of study analysis under section 6.4.1.

Key Changes	Rationale	Contents
Included description of consensus method	Consensus Method has been used to re-read the liver biopsies samples for histological endpoint estimates at Month 18 interim analysis resubmission per FDA agreement. It will be used for subsequent histological analysis for clinical outcomes assessment.	Description of Consensus Method under section 6.2.2.
Added Safety Objectives to be assessed and additional AESIs	Based on the FDA feedback after Month 18 interim analysis submission according to protocol version 11.0 (Dated 04May2021)	Added additional analyses for AESIs under section 10.4.  Added additional analyses based on adjudicated data by Renal, Cardiovascular Diseases and Hepatic Safety Committee under section 10.4
Added Analysis of Covid-19 impact on the study	Following FDA guidance: Conduct of Clinical Trials of Medical Products During the COVID-19 Public Health Emergency	Impact of Covid-19 on protocol deviations under section 5.6  Incidence of Covid-19 infection under section 10.3  Incidences of AEs before and after Covid-19 under section 10.
Updated lab analysis	Per FDA feedbacks, additional lab data analyses related to cardiovascular, renal and hepatic injuries from both local and central laboratories have been produced in Month 18 IA resubmission and will be also done at the end of study	Updated Serum Chemistry Lipids analysis under section 10.4.9.4  Updated Liver Injury related lab data analyses under section 10.5.4.  Updated Renal injury related lab data analyses under section 10.5.6

## **APPENDIX A. DATA CONVENTIONS AND STANDARD PROGRAMMING**

### **DATA PRESENTATION CONVENTIONS:**

The precision of original measurements will be maintained in summaries, when possible. Minimum and Maximum will be presented with the same decimal places as the raw data. Means, medians, SEMs, and SDs will be presented with an increased level of precision, where means, medians, and percentiles will be presented to one more decimal place than the raw data, and the SEMs and SDs will be presented to two more decimal places than the raw data. In general, the decimal places should not exceed 3 decimal places, unless appropriate.

For tables where rounding is required, rounding will be done to the nearest round-off unit. For example, when rounding to the nearest integer, values  $\geq XX.5$  will be rounded up to  $XX + 1$  (eg, 97.5 will round up to 98), while values  $< XX.5$  will be rounded down to  $XX$  (eg, 97.4 will round down to 97).

Percentages based on frequency counts will be based on available data, and denominators will generally exclude missing values. Percentages based on frequency counts will be presented as whole numbers (no decimal places), and values less than 1% will be presented as “<1%.” Values less than 100% but that round up from 99.5% to 100% will be presented as “>99%.”

Quantitative laboratory tests containing less than (<) and greater than (>) symbols are test results that are below and above quantifiable limits, respectively. In order to retain these values for analysis purpose, the following imputations will be done within the analysis datasets:

For laboratory test results that are below the quantifiable limit:

Imputed laboratory results = (numeric portion of the result) x 0.9.

For laboratory test results that are above the quantifiable limit:

Imputed laboratory results = (numeric portion of the result) x 1.1.

Date variables will be formatted as DDMMMYYYY for presentation. Time will be formatted in military time as HH:MM for presentation.

All output will be incorporated into Microsoft Word rich text format (.rtf) files, sorted, and labeled according to the ICH recommendations, and formatted to the appropriate page size(s).

